The primary analyses of efficacy data (IOP) will employ multiple imputation (MI) methods using the Markov Chain Monte Carlo (MCMC) approach to impute missing data and using the last time-consistent observation carried forward (LOCF) to impute data for time points after a subject's primary study eye is prescribed IOP-lowering drops as rescue therapy.

Sensitivity analyses, to determine robustness of results, will be performed using the MCMC approach to impute non-monotone missing information and pattern mixture models control-based pattern imputation for monotone missing information (including data for subjects who drop out prior to the 12 Week Visit and data for time points after a subject's primary study eye is prescribed IOP-lowering drops), LOCF to impute both missing data and data after a subject's primary study eye is prescribed IOP-lowering drops, baseline time-consistent observation carried forward (BOCF) to impute both missing data and data after a subject's primary study eye is prescribed IOP-lowering drops and using observed data only (excluding data after a subject's primary study eye is prescribed IOP-lowering drops as rescue therapy). Additionally, sensitivity analyses will be performed on the PP population using observed data only (excluding data after a subject's primary study eye is prescribed IOP-lowering drops as rescue therapy).

For time-consistent imputations, IOP values missing at an 8AM time point will only be imputed with the IOP value from a previous 8AM time point (last or baseline). Imputations at 10AM and 4PM will be performed similarly.

Definition of Baseline

For IOP, the baseline measure will be defined as the last non-missing time-consistent measure prior to initiation of investigational treatment and after washout of previous IOP medication. In most cases this will be the measure of IOP at Baseline Visit 2. For all other variables, baseline will be defined as the last non-missing measure prior to initiation of investigational treatment. Change from baseline will be calculated as follow-up visit – baseline visit.

Data Analysis Conventions

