$$\text{Total Exposure (days)} = (\text{Date of last recorded visit} - \text{Date of first insertion of a depot in either eye}) + 1$$

Total treatment exposure (days) for each subject exposed to study drug will be summarized with continuous descriptive statistics for each treatment group and for all subjects, using the Safety population. A subject listing of treatment exposure will also be produced.

13. Efficacy Analyses

Primary Analysis

The primary analysis of the primary efficacy outcome will employ a linear model of IOP in the primary study eye of subjects in the FAS. The response variable will be IOP at the given visit (2 Week, 6 Week, and 12 Week) and time point (8AM, 10AM, and 4PM), time point specific baseline IOP will be used as a covariate, and treatment will be the main effect factor. Each time point within each visit will be modeled separately.

IOP refers to the single result from the following procedure. IOP will be assessed by two qualified independent study site personnel at each visit and time point using a Goldmann applanation tonometer affixed to a slit lamp with the subject seated. Two measurements should be performed, and if the IOP is within 1 mm Hg, the average of the first two measurements should be recorded. If the IOP from the first two readings shows a greater than 1 mm Hg difference, a third reading should be taken and the average of all three readings recorded. Averages of readings are calculated within the clinical database.

For the primary analysis, MI methods will use the MCMC approach for any data missing from these visits/time points, after LOCF has been used to impute data for time points after the subject's primary study eye is prescribed IOP-lowering drops. Example MCMC imputation code which will be implemented after LOCF has been applied (SAS® version 9.4) is shown here:

```
PROC MI DATA = indata SEED = 7436892 OUT = outdata NIMPUTE=20;
BY TMPTN;
MCMC INITIAL = EM;
VAR trt baseline WV2 WV4 WV6 WV8 WV10 WV12;
```

RUN;

where

- *indata* is the name of the input dataset;
- *outdata* is the name of the output dataset;
- *nimpute* is the number of imputations;
- *tmpn* is the time point of assessment, 8AM, 10AM, or 4PM;
- *trt* is the name of the treatment group variable in numeric format;
- *baseline* is the average IOP at baseline
- *WV2* is the IOP value for the 2 Week visit;
- *WV4* is the IOP value for the 4 Week visit;
- *WV6* is the IOP value for the 6 Week visit;
- *WV8* is the IOP value for the 8 Week visit;

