- *WV10* is the IOP value for the 10 Week visit;
- *WV12* is the IOP value for the 12 Week visit.

Twenty complete data sets for each time point will be generated from the above code. The data will be transposed to have a vertical structure with one record per subject, imputation, visit, and time point. Each complete data set will be used to compute the mean IOP and analyze using the linear model with time point specific baseline IOP used as a covariate, and treatment as the main effect factor. A separate model will be fit for each visit/time point combination. Then, the SAS® procedure MIANALYZE will be used to analyze the results from the 20 complete data sets to generate a combined inference. The following SAS® code will be used:

```

ODS OUTPUT LSMEANS = outdataB;
PROC MIXED DATA = outdataA;
CLASS trt;
MODEL IOP = trt baseline;
BY visitn tmpn _IMPUTATION_;
LSMEANS trt/PDIFF CL;
RUN;

```

where

- *IOP* is the IOP for each visit and time point;
- *visitn* is the visit number variable in numeric format;
- *tmpn* is the time point variable in numeric format;
- *baseline* is the average IOP at baseline, matched by time point;
- *trt* is the name of the treatment group variable in numeric format;
- *outdataA* is the transposed dataset containing the 20 “complete” datasets from the imputation.

```

ODS OUTPUT PARAMETERESTIMATES = outdataC;
PROC MIANALYZE DATA = outdataB;
MODELEFFECTS ESTIMATE;
STDERR STDERR;
BY visitn tmpn;
RUN;

```

where

- *outdataB* is the name of the output dataset that contains the statistical results of the difference between treatment groups from the MIXED procedure that is run on each of the twenty imputation datasets;
- *outdataC* is the name of the output dataset that contains all the information needed for the table.

After imputation the least squares mean differences (OTX-TP minus PV) will be presented along with 2-sided 95% confidence intervals (CIs) around the difference and 2-sided p-values testing the difference equal to 0. Inference will be made on the 2-sided p-value at a 2-sided alpha = 0.05 at each time point and visit. The study will be considered a success if the 2-sided p-value < 0.05 (demonstrating statistical superiority) and the point estimate of the difference is < 0 at all time points over the three visits.

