- *WV8* is the IOP value for the 8 Week visit;
- *WV10* is the IOP value for the 10 Week visit;
- *WV12* is the IOP value for the 12 Week visit.

Then the following SAS® code will be used to produce twenty “complete” datasets for each time point, imputing monotone missing data using a control-based pattern mixture model:

```
PROC MI DATA = mondata SEED = 48670 NIMPUTE = 20 OUT = outdata
MINIMUM = . . 0 MAXIMUM = . . 70 ROUND = . . 0.25;
BY visitn tmpntn;
CLASS trt;
MONOTONE REG(WV2_8 WV4_8 WV6_8 WV8_8 WV10_8 WV12_8 = baseline /
details);
MNAR model(WV2_8 WV4_8 WV6_8 WV8_8 WV10_8 WV12_8/ MODELOBS =
(TREATMENT="2"));
VAR trt baseline WV2_8 WV4_8 WV6_8 WV8_8 WV10_8 WV12_8;
RUN;
```

After obtaining twenty complete datasets, the data from the two MI procedures will be combined and will then be transposed to have a vertical structure with one record per subject, imputation, visit, and time point. SAS® code similar to what is previously described for multiple imputations in the primary analysis will then be employed to run the model on each dataset and combine results across imputations.

In the case that there is no missing data for a given visit and time point, observed data will be analyzed. Analyses on observed data and without MI methods will use the following statistical models:

```
ODS OUTPUT LSMEANS = outdata;
PROC MIXED DATA = indata;
```

```

CLASS trt;
MODEL IOP=trt baseline;
BY visitn tmptn
LSMEANS trt/PDIFF CL;
RUN;
    
```

where

- *IOP* is the IOP for each visit and time point;
- *visitn* is the visit number variable in numeric format;
- *tmptn* is the time point variable in numeric format;
- *baseline* is the average IOP at baseline, matched by time point;
- *trt* is the name of the treatment group variable in numeric format;
- *indata* is the dataset containing only observed data.

and

```

ODS OUTPUT STATISTICS = outdata;
PROC TTEST DATA = indata;
CLASS trt;
VAR IOP;
BY visitn tmptn;
RUN;
    
```

- *IOP* is the IOP for each visit and time point;
- *visitn* is the visit number variable in numeric format;
- *tmptn* is the time point variable in numeric format;
- *baseline* is the average IOP at baseline, matched by time point;
- *trt* is the name of the treatment group variable in numeric format;
- *indata* is the dataset containing only observed data.

Secondary Analysis

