13.1.1 ADDITIONAL EFFICACY ANALYSES

IOP measures, mean change from baseline, and mean percent change from baseline IOP measures from non-primary visits (4 Week, 8 Week, 10 Week Visits) will be also analyzed similarly to the primary endpoint analysis.

Additionally, to further understand efficacy within each previous ocular anti-hypertensive therapy category, the primary analysis strategy (linear model of IOP Markov Chain Monte Carlo (MCMC) approach to impute missing data and using the last time-consistent observation carried forward (LOCF) to impute data for time points after a subject's primary study eye is prescribed IOP-lowering drops as rescue therapy) will be completed separately for the subgroups (i.e. stratum) of subjects within each previous ocular anti-hypertensive therapy category. The FAS will be used for these subgroup analyses.

All analyses will be presented in summary tables by treatment group. Subject level listings will also show IOP by treatment, time point and visit where appropriate.

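### The primary imputation code puts Weeks 4, 8 and 10 into its 10AM and 4PM runs, where no IOP is scheduled, so part of the stated model behind 6 of the 9 co-required endpoints is not identified

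*SAP*

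**What the plan says.** The primary analysis in SAP v2.0, section 13, first carries the last value forward after rescue and then imputes what is still missing by MCMC. The code runs by a time-point variable that "is the time point of assessment, 8AM, 10AM, or 4PM", and every run uses the same list: "VAR trt baseline WV2 WV4 WV6 WV8 WV10 WV12". The text then commits to that code for all three clock times: "Twenty complete data sets for each time point will be generated from the above code". Next, "The data will be transposed to have a vertical structure with one record per subject, imputation, visit, and time point", and a separate model is fitted to each visit and time-point combination.

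The block is introduced as an example, but as one that will be implemented. The same sentence pair limits the imputation to data missing at the primary visits and time points. No other list is given for 10AM or 4PM.

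The imputation model is bypassed only in one situation: "In the case that there is no missing data for a given visit and time point, observed data will be analyzed".

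Protocol section 4.5.7.9.1 and the synopsis place IOP at the 4, 8 and 10 Week Visits at 8AM alone. Readings at 10AM and 4PM are scheduled only at Weeks 2, 6 and 12.

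Three other places in SAP v2.0 bear on the point:
- Section 9 keeps carry-forward within clock time and adds that "Imputations at 10AM and 4PM will be performed similarly". It does not mention unscheduled cells.
- Section 13.1.1 says that IOP, change and percent change "from non-primary visits (4 Week, 8 Week, 10 Week Visits) will be also analyzed similarly to the primary endpoint analysis", with no limit to 8AM.
- The control-based pattern-mixture analysis repeats the full list in its first step. Its second step uses "VAR trt baseline WV2_8 WV4_8 WV6_8 WV8_8 WV10_8 WV12_8", which names 8AM variables only.

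**The concern.** In the 10AM and 4PM runs, the columns for Weeks 4, 8 and 10 contain no scheduled observation for any subject. A multivariate normal model cannot learn a mean, a variance or a covariance for a variable that is never observed, so the model as written has no unique fit for those three columns.

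Three things are at stake. First, the run may stop, or finish on a near-singular covariance matrix. The analyst would then have to choose a replacement for the primary imputation model after the SAP is final, in a trial where one failed test out of nine means failure. Second, the code as written would output imputed 10AM and 4PM values at Weeks 4, 8 and 10. These are six visit and time-point combinations (3 visits × 2 times) with no measured data, and neither section 13.1.1 nor the title of Table 14.2.1.2 keeps them out. Third, the SAP does not say whether post-rescue carry-forward creates values in those cells. If it does, each one is an exact copy of an earlier visit, which makes the near-singularity worse.

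**Working it through.** **1. Will the imputation model be needed?** SAP section 6 plans for 10% discontinuation: 294/0.9 ≈ 327 and 196/0.9 ≈ 218, rounded to about 330 and 220. Some Week 12 values will therefore be missing, and the observed-data route is unlikely to apply.

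**2. The plan's own power figure.** With SD 3.75, difference 1.5 and 294/196 subjects, the standard error is 3.75 × √(1/294 + 1/196) = 0.346. Then 1.5/0.346 = 4.34, and power per test is Φ(4.34 − 1.96) = 0.991. Under independence, 0.9913⁹ = 0.924, so the stated figure above 90% is reproduced. Nothing below changes it.

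**3. Endpoints affected.** 3 visits × 2 clock times (10AM, 4PM) = 6 of 9. The three 8AM endpoints are unaffected, because all six visits have an 8AM reading.

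**4. Parameter count per 10AM or 4PM run.**
- Stated list, 8 variables: 8 means + 8×9/2 = 36 variances and covariances = 44.
- Variables with scheduled data (`trt`, `baseline`, Weeks 2, 6, 12): 5 + 5×6/2 = 5 + 15 = 20.
- Not identified: 44 − 20 = 24. Directly: 3 means, 3 variances, 3 covariances among the empty columns, and 3×5 = 15 with the others.

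This count does not depend on the software.

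**5. What the likelihood does with the empty columns.** EM on simulated 10AM data returned, for the three empty means, whatever starting value was supplied (5, 15, 23, 30 or 60 mmHg). The block for treatment, baseline and Weeks 2, 6 and 12 equalled the five-variable fit to below 10⁻¹⁴. So the unidentified part does not contaminate the endpoint block.

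**6. What MCMC may do (illustration only; Python, not SAS).** The assumptions, which the documents do not give, were: 490 subjects (294/196); values missing completely at random at 2%, 5% and 10% at Weeks 2, 6 and 12; correlation 0.5 to 0.7; a Jeffreys prior; an EM start; 200 burn-in iterations, 100 between imputations and 20 imputations, that is 200 + 19×100 = 2,100 iterations. A run counted as stopped when a covariance factorisation failed at double precision.
- Eight variables: 19 of 40 runs plus 16 of 30 runs stopped, 35 of 70 in all. The other 35 ended with condition numbers of 5×10¹² to 8×10¹⁶.
- Five variables: 80 of 80 finished, with condition number at most 316.
- In a separate set of six eight-variable runs (490 or 550 subjects), the smallest eigenvalue of the correlation matrix fell from about 0.3 to between 10⁻⁸ and 3×10⁻⁷ by iteration 1,000. Five runs broke down, between iterations 1,833 and 4,821, so some would have outlasted a 2,100-iteration schedule.

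**7. Effect on the endpoints.** In the 21 completed eight-variable runs that had a paired five-variable fit (40 − 19), treatment differences at Weeks 2, 6 and 12 moved by at most 0.07 mmHg and standard errors by at most 0.014. Repeating the five-variable fit with other random numbers moved them by up to 0.08 mmHg and 0.014. No effect is distinguishable from imputation noise.

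**8. If carry-forward fills the unscheduled cells** (assumed 5%, 10% or 20% of subjects rescued; 490 or 550 subjects), EM met a singular matrix in 5 of 6 cases. In the sixth the smallest eigenvalue was 6×10⁻⁹ by iteration 200.

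**The case against.** The best defence is that nothing the trial will be judged on is shown to move. The unidentified quantities are nuisance parameters of three columns that feed no primary test. The prose restricts imputation to the primary visits and times, and the block is called an example. Other code in the section is plainly a template: the second pattern-mixture step refers to a treatment variable under a different name from its class variable, and it runs by visit on data that have one column per visit. A competent programmer would probably drop the empty columns.

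Most of this stands, and it limits the point. It does not remove it. The text says the example will be implemented and that each time point's data sets come from it. Restricting which values are wanted does not take Weeks 4, 8 and 10 out of the model. The repair is left unwritten.

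A reader might go further in four ways that the documents do not support:
- *The six endpoints cannot be estimated, or are biased.* Their block stays identified and equals the five-variable fit.
- *The run will fail.* The documents do not give the prior or the iteration count, and they do not show how the software treats an all-missing column. It might reject or drop such columns at the start. The failure counts above describe one program under stated assumptions.
- *Invented values will be reported at Weeks 4, 8 and 10.* No planned output clearly asks for 10AM or 4PM results there. The wording merely does not exclude them.
- *SAP v2.0 lost a safeguard.* SAP v1.0 did note, in its pattern-mixture legend, that Weeks 4, 8 and 10 have only 8AM data, and v2.0 lacks that note. But v1.0's primary block had the same list, and so did its first pattern-mixture step.

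**Conclusion.** The point holds as an error in the stated specification. For 10AM and 4PM, the primary imputation model includes three of eight variables with no scheduled data, and 24 of 44 parameters are not identified. This rests only on the SAP code and the protocol schedule. It affects the runs behind 6 of the 9 co-required endpoints but not, on the evidence here, their estimates, standard errors or power.

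The consequence is conditional. The pre-specified run may stop or become unstable, so that a substitute has to be chosen without pre-specification. Values for never-measured cells may also be carried into the non-primary-visit outputs. Whether either happens depends on software behaviour and programming choices that the documents do not settle. It should be corrected because the correction is easy and the primary analysis should run as written; it is not a reason to doubt the design.

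**What to change.** Amend SAP section 13 and the related text before treatment codes are unmasked:

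1. Keep the full variable list for the 8AM run. For 10AM and 4PM, write `VAR trt baseline WV2 WV6 WV12`.
2. In section 9, state that post-rescue carry-forward does not create 10AM or 4PM values at Weeks 4, 8 and 10.
3. In section 13.1.1 and Table 14.2.1.2, state that the Week 4, 8 and 10 analyses are at 8AM only.
4. Make the same split by clock time in both pattern-mixture steps, and write out the 10AM and 4PM variable names in the second.

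A trial run on masked or dummy data would confirm that all three clock times complete. The cost is a few lines of text and code. Data collection, endpoints, success rule and sample size do not change.

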Two-sample t-test p-values and two-sided 95% CI's will also be computed around the difference (OTX-TP minus PV) in IOP between treatment groups at each time point and visit for the primary analysis data (FAS employing MI methods using MCMC approach to impute missing data and using LOCF to impute data for time points after a subject's study eye is prescribed IOP-lowering drops as rescue therapy). The following SAS® code will be used for the t-test:

```

ODS OUTPUT STATISTICS = outdataB;
PROC TTEST DATA = outdataA;
CLASS trt;
VAR IOP;
BY visitn tmpn _Imputation_;
RUN;

```

- *IOP* is the IOP for each visit and time point;
- *visitn* is the visit number variable in numeric format;
- *tmpn* is the time point variable in numeric format;
- *baseline* is the average IOP at baseline, matched by time point;
- *trt* is the name of the treatment group variable in numeric format;
- *outdataA* is the transposed dataset containing the 20 "complete" datasets from the imputation.

Then, as with the PROC MIXED results, the SAS® procedure MIANALYZE will be used to analyze the results from the 20 complete data sets to generate a combined inference.

```
ODS OUTPUT PARAMETERESTIMATES = outdataC;  
PROC MIANALYZE DATA = outdataB;  
MODELEFFECTS ESTIMATE;  
STDERR STDERR;  
BY visitn tmptn;  
RUN;
```

where

- *outdataB* is the name of the output dataset that contains the statistical results of the difference between treatment groups from the MIXED procedure that is run on each of the twenty imputation datasets;
- *outdataC* is the name of the output dataset that contains all the information needed for the table.

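### SAP v2.0's primary-analysis code saves and pools the two arm means, not the OTX-TP minus PV difference that its own text and success rule require

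*SAP*

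**What the plan says.** All of this is in SAP Version 2.0, Section 13, Primary Analysis.

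- **Status of the code.** The PROC MI block is labelled an example. The modelling and pooling block after it is not; it is introduced by "The following SAS® code will be used".
- **Model step.** PROC MIXED asks for the treatment comparison with "LSMEANS trt/PDIFF CL". The only table sent to a dataset is the one named in "ODS OUTPUT LSMEANS = outdataB".
- **Pooling step.** PROC MIANALYZE reads `outdataB`, takes `ESTIMATE` as the effect and `STDERR` as its standard error, and runs by visit and time point. It has no row selection and no treatment variable.
- **Legend.** The text says `outdataB` "is the name of the output dataset that contains the statistical results of the difference between treatment groups".
- **Decision rule.** Success needs a two-sided p-value below 0.05, and it needs that "the point estimate of the difference is < 0 at all time points over the three visits".
- **t-test block.** It saves a whole table, "ODS OUTPUT STATISTICS = outdataB", and passes it to the same pooling call. Its legend describes the input as "the statistical results of the difference between treatment groups from the MIXED procedure that is run on each of the twenty imputation datasets", although it comes from PROC TTEST.
- **Observed-data block.** It also saves only the least squares means ("ODS OUTPUT LSMEANS = outdata"), but pools nothing.

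**The concern.** The code and the text beside it cannot both be followed. The text defines the result as a between-group difference. The code passes on a table with one row per arm, and the pooling step treats those rows as repeated imputations of a single parameter.

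The block serves all nine co-primary tests. The control-based sensitivity analysis uses similar code. The secondary endpoints and non-primary visits are analysed in the same way, and the primary strategy is repeated within each stratum. SAP Section 1 also says the SAP's methods supersede the protocol's.

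The same LSMEANS statement stood in SAP Version 1.0. The Version 2.0 revision history records typographical corrections to the Primary Analysis subsection, but this statement was left in place.

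The practical risk is a programming error in the confirmatory analysis, or a programmer departing without documentation from code the signed SAP says will be used.

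**Working it through.** **Inputs from SAP Section 6:** SD 3.75 mmHg, difference 1.5 mmHg, 294 OTX-TP and 196 PV subjects, two-sided alpha 0.05, independent time points. **From Section 13:** 20 imputations.

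**Assumptions.** The documents give no follow-up arm means, so the PV mean is set at 18, 22 or 26 mmHg. SD 3.75 is taken as the residual SD. Variation between imputations within an arm is ignored. That the LSMEANS table has one row per arm is general SAS behaviour, not something the SAP states.

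**The plan's own figure first.** The SE of the difference is 3.75 x sqrt(1/294 + 1/196) = 0.346. Power per time point is 0.9913, and 0.9913^9 = 0.924. The stated power above 90% reproduces and is not in dispute.

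**What the printed code pools.** Each visit and time point supplies 2 arms x 20 imputations = 40 rows. Write d for the true difference (OTX-TP minus PV). Rubin's rules with M = 40 give:

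- Pooled estimate = PV mean + d/2
- Within variance W = 3.75² x (1/294 + 1/196)/2 = 0.0598
- Between variance B = (40/39) x (d/2)² = (40/39) x 0.5625 = 0.577 at d = -1.5
- Total T = W + (1 + 1/40) x B = 0.0598 + 0.5913 = 0.651, so SE = 0.807
- df = 39 x (1 + 0.0598/0.5913)² = 47

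| Assumed PV mean | Value returned as coded | t | Intended target |
|---|---|---|---|
| 18 | +17.25 (SE 0.81) | 21.4 | -1.5 (SE 0.35) |
| 22 | +21.25 (SE 0.81) | 26.3 | -1.5 (SE 0.35) |
| 26 | +25.25 (SE 0.81) | 31.3 | -1.5 (SE 0.35) |

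Every p-value in the coded column is below 0.0001, but it tests whether the midpoint of the arm means is zero. With 330 and 220 subjects the two SEs become 0.80 and 0.33.

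**Sign.** PV mean + d/2 is negative only if the PV mean is below 0.75 mmHg (below 1.5 mmHg if d = -3).

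**Check with imputation noise.** A separate simulation assumed a between-imputation SD of 0.08 mmHg per arm and PV means of 20 to 25 mmHg. The printed code gave about 19.2 to 25.7 mmHg with p < 0.0001, whether the true benefit was 1.5, 0 or -1.5 mmHg. Pooling the 20 differences instead gave about -1.5 (SE about 0.36, 95% CI about -2.2 to -0.8) for a 1.5 mmHg benefit. With no effect it gave about 0 (p 0.97 to 0.99).

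**t-test block.** From general SAS knowledge, the STATISTICS table holds per-arm rows as well as two difference rows. If all four were pooled, the same simulation gave about 9 to 14 mmHg with SE about 10 to 13. More probably the step stops with an error, because that table is not expected to have a column named ESTIMATE. Either way it does not deliver the treatment difference.

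**The case against.** The prose leaves nothing undecided. Section 13 states the model, the estimand, the null value and the success rule, Section 9 fixes the direction of subtraction, and the legend says what `outdataB` should contain. On this view the slip is one table name.

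The printed blocks are excerpts rather than a program: the transpose between imputation and modelling, for example, is described only in words. No one would report a treatment difference of +17 to +25 mmHg, so the error creates no false-positive risk. The t-test is additional to the linear model that decides success. The SAP also undertakes to describe in the study report any changes to planned analyses made after unmasking.

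Most of this stands, and it limits the weight of the point. The estimand is not in doubt. Alpha, power and sample size are unaffected, and validation would probably catch the error. The observed-data block, which pools nothing, yields no wrong number.

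It does not remove the error. The modelling and pooling code is presented as the code to be used, so a programmer who does what the text wants must depart from it, and that departure should be settled before unmasking. The printed code also leaves open which t-test difference row is pooled, and it does not state the `trt` coding that fixes the sign.

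**Conclusion.** The concern holds. As written, the primary-analysis code contradicts the text around it and would return the midpoint of the two arm means instead of the treatment difference. At the SAP's planning values that is +17.25 to +25.25 mmHg against a target of -1.5 mmHg. The exact values depend on the assumed PV means. The conclusion does not, since the returned value is positive at any plausible IOP and the success rule could not be met.

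The t-test pooling step has a related fault in failing to select the difference, and its legend names the wrong procedure. This should be fixed before analysis. It is a specification error in the code and does not undermine the design.

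**What to change.** 1. In the primary block and the observed-data block, save the differences table (`DIFFS=`) and the least squares means to separate datasets. State the `trt` coding so that the sign is OTX-TP minus PV. The control-based code takes treatment 2 as its reference, which implies PV = 2.
2. Pool only the differences for inference. Pool the least squares means by visit, time point and treatment for the per-arm figures listed in Section 24.
3. In the t-test block, keep one prespecified between-group row (pooled or Satterthwaite), map its estimate and standard error to the names PROC MIANALYZE reads, and correct the legend.
4. As a minor tidy-up, with no effect on results claimed: in the 10AM and 4PM imputation runs list only Weeks 2, 6 and 12, because Protocol 4.5.7.9.1 schedules Weeks 4, 8 and 10 at 8AM only. Add 10AM and 4PM versions of the control-based step, which now names only 8AM variables.

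The cost is SAP code and legend wording. No new data are needed, and the estimand, population, test and success rule do not change.
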